7.1 Participant withdrawal criteria

Participants may be terminated early from the study for the following reasons:

- a. The participant elects to withdraw consent from study activities.
- b. The participant dies.
- c. The participant has a serious allergic or anaphylactic reaction to the study drug
- d. The participant's condition deteriorates significantly necessitating either a transfer to the intensive care unit (ICU) or the need for advanced respiratory support (high flow oxygen ≥ 15 L/minute, CPAP, non-invasive or invasive mechanical ventilation), and the treating clinician thinks it is in the best interest of the patient to be withdrawn \pm unblinded. If the patient is unblinded, any open label use of sirolimus after that will be based on clinical grounds at the discretion of the treating clinician(s). The study drug (sirolimus or placebo) will continue for the maximum stipulated duration of 14 days regardless of escalation in care, unless the patient is withdrawn from the study.
- e. In the opinion of the investigator, it is not in the participant's best medical interest to continue to participate in the study.

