4.1 Main Study Objective

The main objective of our study is to determine if treatment with sirolimus can improve clinical outcomes in hospitalized patients with COVID-19.

4.2 Primary Endpoint:

Progression to respiratory failure requiring advanced support measures, either due to inadequate ventilation (non-invasive or invasive mechanical ventilation) or inadequate oxygenation (CPAP* or high flow supplemental oxygen at rates \geq 15 liters/minute), in patients given sirolimus compared to the placebo group.

4.3 Secondary Endpoints:

Key secondary endpoints:

- Escalation in level of care
- Increase in total lymphocyte count
- Normalization of biomarkers (Ferritin, LDH, and d-dimer)
- Survival to hospital discharge
- Drug safety profile (Incidence and type of adverse and serious adverse events)

Other outcomes measures:

- Fever
- Duration of advanced respiratory support
- Duration of hospital stay (in survivors)
- Time from treatment initiation to death (in non-survivors)
- Need for initiation of other off-label rescue therapies such as Anti IL-6 agents, at the discretion of treating clinicians

* CPAP use for known obstructive sleep apnea will not be considered as disease progression.

5. Study Design

We will employ a randomized, double blind, placebo-controlled study design. 30 patients hospitalized with COVID-19 and meeting the inclusion criteria specified below will be randomized to receive sirolimus or placebo in a 2:1 manner. The treatment regimen and duration are provided in Sections 5.5 and 5.6.

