6.1 Study and Timeline Overview

Patients will be identified by the medical and research staff at the University of Cincinnati Medical Center and the facilities of the affiliated health systems UC Health, LLC and University of Cincinnati Physicians Company, LLC. Recruitment will take place until 30 evaluable patients have been enrolled, or the incidence of new cases does not permit further enrollment. Patients who meet eligibility criteria, provide informed consent and are enrolled in the study will receive instructions regarding study drug dosage, route and administration. The study drug will be given each morning along with other inpatient medications at roughly the same time every day. Patients will be on the study drug for a maximum duration of 14 days, or until hospital discharge, whatever happens first. In case a patient progresses to require advanced respiratory support, the study drug can continue as scheduled at the discretion of the treating clinician(s). If deemed clinically necessary on a case-by-case basis, in these scenarios the patient may need to be withdrawn ± unblinded.

All study procedures will take place after obtaining informed consent. Details of the informed consent process are provided in Section 6.3. Prior to starting study drug, baseline demographic and clinical variables will be collected along with vital signs, amount of supplemental oxygen required, laboratory biomarkers such as absolute lymphocyte count, ferritin, LDH, and d-dimer, renal and liver function tests, concomitant medications, past medical history, and results of the chest imaging. After study initiation, chart reviews will be conducted on a daily basis to assess vital signs, changes to concomitant medications, lab values, and oxygenation indices. Study-specific biomarkers: absolute lymphocyte count, serum ferritin, d-dimer and LDH will be measured at Day 3, 7 and 14 following study initiation, unless already checked clinically in the 24 hours prior to the testing time.

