12.3.2 Dose Reduction

Any AE of \geq Grade 3 and attributed as possibly, probably or definitely related to sirolimus will result in the dose being held until the AE has resolved to \leq grade 1 or baseline. If the AE resolves, reinstitution of treatment can occur but at a reduced dose of 1mg daily. If the AE recurs at the reduced dose, treatment will be held and the subject will be withdrawn from the study. Of note, an escalation in patient's level of care (e.g. floor to ICU) or the need for advanced respiratory support will not automatically result in dose reduction of the study drug, unless deemed necessary for patient safety by the PI or the treating clinicians feel it is in the patient's best interest to be withdrawn \pm unblinded. In case the dose of study drug is altered in a subject, in order to maintain blind, a corresponding change will also be made in a placebo subject. Toxicities that may be attributable to sirolimus are listed in Sections 9.1 and 14.3.6. If

any of these AEs occur at grade ≤ 2 , sirolimus may be continued and the AE managed with supportive care. For any AE with a grade ≥ 3 , the rules outlined in Sections 14.2 – 14.10 apply for holding of dose, dose reduction, removal from study and reporting requirements.

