13.1.2 Subject discontinuation

An intent-to-treat approach will be used. All data acquired prior to termination for the reasons outlined below will be included in the primary analysis unless patient withdraws consent. Every effort will be made to conduct a final study visit with the participant and participants will be followed clinically until, if applicable, all AEs attributable to study drug resolve. Please refer to Section 7.1 for a list of the reasons that may lead to participant withdrawal from the study.

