13.1.4 Individual early stopping rules

A study participant will be terminated from the study if any of the following occurs during the study:

- Recurrent or persistent sirolimus-related toxicity unresponsive to treatment in spite of dose adjustments.
- Pregnancy
- The participant refuses to continue in the study
- The investigator determines that the participant should be withdrawn from the study for reasons not listed above

A subject will be considered evaluable if they took one dose of the study drug. Subjects who are withdrawn before initiating treatment will be considered as premature discontinuation, and will be replaced by another participant.

Every effort will be made to obtain endpoint evaluations for subjects who withdraw or who discontinue prematurely from the study. The same evaluations performed at final visit will be completed at the time of termination. If withdrawal is due to inability to tolerate investigational drug or other untoward event related to investigational drug, the withdrawal will be noted in data analysis as treatment failure.

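### Under 7.1(d), an ICU transfer short of advanced respiratory support can end participation before the primary event is decided, and no clause expressly says a later event will be counted

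*Combined protocol and SAP*

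**What the plan says.** Section 7.1 lists reasons for terminating a participant early from the study. Item (d) applies when the patient's "condition deteriorates significantly necessitating either a transfer to the intensive care unit (ICU) or the need for advanced respiratory support", and the treating clinician judges withdrawal, with or without unblinding, to be in the patient's best interest. After unblinding, "any open label use of sirolimus after that will be based on clinical grounds at the discretion of the treating clinician(s". The default is the opposite: study drug continues for up to 14 days despite escalation of care, unless the patient is withdrawn.

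The primary endpoint in 4.2 is "Progression to respiratory failure requiring advanced support measures": ventilation, CPAP, or high-flow oxygen at 15 L/min or more. ICU transfer is not a component. "Escalation in level of care" is a separate key secondary endpoint in 4.3.

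Section 6.1 discusses only patients who already need advanced respiratory support: "If deemed clinically necessary on a case-by-case basis, in these scenarios the patient may need to be withdrawn". Section 12.3.2 is wider. It names a floor-to-ICU move, says this does not automatically reduce the dose, and makes an exception where "treating clinicians feel it is in the patient's best interest to be withdrawn".

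On data after withdrawal, 13.1.2 states an intent-to-treat approach and adds: "All data acquired prior to termination for the reasons outlined below will be included in the primary analysis unless patient withdraws consent". Section 13.1.4 says: "Every effort will be made to obtain endpoint evaluations for subjects who withdraw or who discontinue prematurely from the study". Its next sentence has the final-visit evaluations done at termination. The SAP repeats section 15 of the protocol and adds no rule on withdrawal, unblinding or open-label sirolimus.

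**The concern.** The trigger in 7.1(d) is wider than the primary event. A patient on conventional oxygen below 15 L/min who moves to the ICU has met the secondary endpoint but not the primary one. At that point the plan allows the clinician to end participation, learn the allocation and start open-label sirolimus.

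Two things are at stake. The first is ascertainment. If the patient needs ventilation or high-flow oxygen afterwards, the plan does not clearly say that the event is collected and counted. Such patients are deteriorating, so they are plausibly among the likelier ones to have the event. The second is interpretation. The trial is described as double blind, and its outcome is a clinician's decision to start support, which could now be made with the allocation known. A placebo patient may also be on sirolimus by then. Under intent-to-treat, that crossover shrinks the randomised difference; it does not create a false benefit.

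**Working it through.** **Step 1: which clauses would capture a primary event after a 7.1(d) withdrawal?**

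| Clause | What it provides | Expressly covers this patient? |
|---|---|---|
| 6.3 (subsequent visits), 8.5 | Daily chart review, including advanced-support status | Not excluded, but withdrawn patients are not named |
| 6.3 (stays beyond 14 days), 6.2 footnote 7 | Chart monitoring after the study period | Written for long stays and long-term outcomes |
| 8.3 | Day 14 laboratory assessments on the day of withdrawal | Ends at withdrawal |
| 13.1.4 | Best effort for endpoint evaluations; final-visit evaluations at termination | Best effort only, with timing set at termination |
| 13.1.4, treatment-failure rule | Applies to drug intolerance or drug-related events | Not to withdrawal for clinical deterioration |
| 13.1.2, 15, SAP | Intent-to-treat; data before termination included | Nothing on data after termination |
| 13.2 | Follow-up to discharge, resolution or PI decision | Adverse-event withdrawals only, for safety |
| 6.6 | Record review for up to two years after withdrawal or completion | Only if the patient opts in |

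The daily chart review is the nearest safeguard, because it already records the right variable and does not depend on taking study drug. What is missing is a statement that it continues after withdrawal and that the result counts. Section 6.6 makes the reader doubt that it does, since it treats record review after a patient leaves the study as an optional permission.

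**Step 2: the plan's own figure.** Inputs from section 15: 0.50 on placebo, 0.25 on sirolimus, 30 patients at 2:1 (10 and 20), two-sided 80% interval, z = 1.2816. The plan names no interval method, so an uncorrected Wald interval is assumed. The placebo number at which the expected interval just excludes zero is

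n = z² × (0.50×0.50 + 0.25×0.75/2) / 0.25² = 1.6424 × 0.34375 / 0.0625 = 9.03,

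which, taken up to 10, gives 10 + 20 = 30.

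**Step 3: one outcome changed.** The interval is d ± z × √[p₁(1−p₁)/n₁ + p₂(1−p₂)/n₂], where d is placebo minus sirolimus.

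- Planned counts, 5/10 vs 5/20: d = 0.25, SE = √(0.025 + 0.009375) = 0.1854, interval 0.012 to 0.488.
- One later placebo event scored as a non-event, 4/10 vs 5/20: d = 0.15, SE = √(0.024 + 0.009375) = 0.1827, interval -0.084 to 0.384.
- The same patient excluded instead, 4/9 vs 5/20: d = 0.194, interval -0.051 to 0.440.
- One later sirolimus event scored as a non-event, 5/10 vs 4/20: d = 0.30, interval 0.067 to 0.533.

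The plan calls the difference clinically meaningful if the interval excludes zero. One lost placebo event reverses that conclusion, and one lost sirolimus event strengthens it.

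**Step 4: crossover.** Suppose one of ten placebo patients starts open-label sirolimus before the event and gets the full assumed effect. The expected placebo proportion becomes (9×0.50 + 0.25)/10 = 0.475, and the expected difference falls from 0.25 to 0.225. The number and the effect are both assumptions.

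**The case against.** The strongest reply is that the protocol already does most of this. Sections 6.3 and 8.5 review the chart daily for advanced-support status, and the primary endpoint is read from the inpatient chart, not from a final-visit test. Section 13.1.2 says that data before termination are included; it does not say that later data are excluded, and it opens with intent-to-treat. The visit and laboratory timing in 8.3 and 13.1.4 need not govern an outcome taken from the chart. The route is also narrow. It needs ICU transfer below the 15 L/min threshold, a judgement that withdrawal is best, then optional unblinding, then a decision to give sirolimus. Section 6.1 contemplates withdrawal only after advanced support, when the event has already occurred.

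Much of this stands. A reader might infer that the plan discards events after withdrawal. The text does not say so; it is silent, and the fair description is ambiguity. A reader might also infer that the missing code-break procedure, or the lack of a limit on who learns the allocation, is an error. Unblinding for a patient's welfare is ordinary, and a procedure may sit in pharmacy documents that are not public. Tighter rules there would be good practice, not a correction.

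What does not stand is that intent-to-treat settles the matter. It fixes the arm in which a patient is analysed but cannot supply an outcome nobody was told to collect. The best-effort sentence is followed directly by one that places evaluation at termination.

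**Conclusion.** The point holds as a gap in wording with a real consequence. Section 7.1(d) can end participation before the primary event is decided, and no clause expressly commits to following and counting that patient's later event.

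The documents give neither its frequency nor its direction. The one-patient result (0.012 to 0.488 becoming -0.084 to 0.384) rests on the assumed Wald interval and on outcomes falling exactly at the planned counts. Any single changed placebo outcome would do the same, so it shows the fragility of 30 patients and measures neither unblinding nor bias. A reader might infer that the trial is tilted toward finding a benefit; the documents do not support that. Crossover dilutes the difference, and lost events could move it either way. This is an inexpensive improvement to the plan, not a defect that undermines it.

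**What to change.** - **7.1(d), with 6.1 and 12.3.2 aligned:** make clinical deterioration a reason to stop study drug, with or without unblinding, and not a reason to terminate the patient from the study.
- **13.1.2 and the SAP:** state that every randomised, treated patient who is taken off drug, unblinded or given open-label sirolimus stays under the existing chart review for advanced respiratory support through hospital discharge. State that the patient is analysed in the randomised arm with later events counted, unless consent is withdrawn. Discharge is the natural horizon, because section 15 sets the expected control rate over the hospital stay.
- **Consent:** make sure the main form covers this in-hospital review, since the 6.6 permission is optional. The form was not available, so it may already do so.
- **Reporting:** give the numbers unblinded and given open-label sirolimus by arm, before and after the primary event.

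Whether open-label sirolimus is appropriate remains a clinical decision. The cost is protocol and possibly consent wording, plus modest extra chart abstraction in what are likely to be few patients. Open-label use needs recording too, because 12.3.3 covers medications only during the study.

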7.2 Criteria for terminating the study

Up to 30 patients will be enrolled in this study. The maximum duration of patient participation is 14 days. In the event of any death or Grade IV Serious adverse event (SAE) that is unexpected and attributable to the study agent, enrollment will be suspended, pending Data Safety Monitoring Board (DSMB) review.

8. Study variables and measuring methods

8.1 Vital signs

We will abstract the following vital signs from electronic health record review of study subjects daily throughout the study duration: heart rate, blood pressure, and temperature.

Heart rate: The average (mean) heart rate in the 24-hour time frame corresponding to a calendar date will be recorded as that day's heart rate.

Blood pressure: The average (mean) Mean arterial blood pressure (MAP) in the 24-hour time frame corresponding to a calendar date will be recorded as that day's blood pressure. We anticipate MAP to be available in all subjects' medical charts. However, in case MAP is not recorded then we will calculate it based on this formula:

$$\text{MAP} = [2 \times (\text{diastolic blood pressure}) + 1 \times (\text{systolic blood pressure})]/3$$

Temperature: The highest temperature (in degrees Fahrenheit) in the 24-hour time frame corresponding to a calendar date will be recorded as that day's temperature.

8.2 Oxygenation indices

We will abstract the following oxygenation indices from electronic health record review of study subjects daily throughout the study duration: peripheral blood oxygen saturation and fraction of inspired oxygen (FiO₂).

Oxygen saturation: The average (mean) oxygen saturation in the 24-hour time frame corresponding to a calendar date will be recorded as that day's oxygen saturation.

FiO₂: FiO₂ (%) will be recorded if directly available from chart review such as in patients on ultra-high flow devices (e.g. vapotherm, optiflow etc.) or in patients on advanced respiratory support. For all other patients, FiO₂ (%) will be calculated based on the following conversion table provided below and also in Section 6.2. The average (mean) FiO₂ in the 24-hour time frame corresponding to a calendar date will be recorded as that day's FiO₂.

Supplemental O ₂ (l/min)	0	1	2	3	4	5	6	7	8	9	10	11	12	13	14
FiO ₂ (%)	21	24	27	30	33	36	39	42	45	48	51	54	57	60	63

Table: FiO₂ conversion based on supplemental oxygen needs

8.3 Laboratory parameters

The following laboratory parameters will be obtained for our study: CBC (total WBCs, Hb, Platelets), absolute lymphocyte count, AST, ALT, serum creatinine, LDH, ferritin and d-dimer. These labs will be obtained at baseline (within 24 hours of study drug initiation) and at days 3, 7 and 14. In case these labs were drawn in the 24 hours prior to the study stipulated time on

clinical grounds, then we will use those values for the study. If not drawn clinically in the preceding 24 hours, then we will obtain these values as research tests. If COVID-19 biorepository sample obtained on the day of these tests, they can be postponed to the next day. In case a subject is discharged from the hospital prior to the 14-day period or is withdrawn from the study, we will make all efforts to perform the Day 14 assessments on that day.

8.4 Urine pregnancy test

For women of childbearing potential, we will obtain a urine pregnancy test, if not already obtained during the hospitalization prior to study enrollment.

8.5 Other study parameters

Daily chart reviews will be performed to record other variables of interest:

Need for advanced respiratory support: Recorded as Yes/No and type, whether high flow oxygen \geq 15 liters/minute, CPAP, non-invasive, or invasive mechanical ventilation. If a patient receives more than one form of advanced respiratory support in the same day, (e.g. started on non-invasive and worsens to require invasive ventilation, or extubated from invasive to non-invasive ventilation), we will designate the most advanced form of ventilation (in the above scenarios – mechanical ventilation) for that day. The ranking order for the above modes of respiratory support are (from most advanced to least advanced means): 1. Mechanical ventilation, 2. Non-invasive ventilation (e.g. bilevel), 3. CPAP, 4. High flow supplemental oxygen \geq 15 L/minute. Of note, the use of CPAP employed to treat pre-existing obstructive sleep apnea will not count as advanced respiratory support.

Duration of advanced respiratory support: For patients who progress to require advanced respiratory support, the type(s) of support and the time spent on the support (individual modes as well as cumulative, days) will be recorded.

Vital status: The vital status (alive/deceased) will be recorded at study termination as well as at the time of hospital discharge (in case that happens after the 14-day study period). For non-survivors, the time from study initiation to death will also be recorded.

Duration of hospital stay (days): will be recorded starting from the day of admission to the day of hospital discharge. This parameter will only be used for analysis in patients who survive the hospital stay.

9. Risks

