5.1 Identification and Screening

Patients will be identified by the medical staff that cares for patients with COVID-19 at the University of Cincinnati Medical Center and the facilities of the affiliated health systems UC Health, LLC and University of Cincinnati Physicians Company, LLC. In addition, the study staff will actively screen for potential subjects by chart reviews of the patients admitted on the COVID units and based on automated alerts generated on patients under investigation for COVID-19. Identification and screening will take place until 30 evaluable patients have been enrolled, or the incidence of new cases does not permit further enrollment. Potentially eligible patients will be approached by the study investigators, and then by study staff. In order to limit staff exposure to patients with COVID-19 as well as to protect critical personal protective equipment (PPE), study investigators will communicate with potential subjects remotely via telephone rather than in-person visits, as much as possible. Potential patients will be informed about the study, and following completion of the informed consent process, a screening evaluation will be performed. The patient will provide informed consent before any study procedures are performed. Patients who learn of the study from the study listing on ClinicalTrials.gov or from any other source will also be able to be screened for enrollment.

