Data Analysis Plan: The primary endpoint of this study is progression to respiratory failure requiring advanced support measures. The difference in proportions of progression between the placebo and sirolimus groups and the 80% confidence interval will be calculated. If the confidence interval for the difference in proportions does not include zero, then we will conclude that the treatment difference is clinically meaningful. Considering the small sample size of our study, the significant impact of age and other pre-existing conditions such as diabetes mellitus on overall prognosis in patients with COVID-19 cannot be accounted for in the primary analysis. Patients will be randomized according to a computer-generated permuted block randomization stratified on age: <50 years, 50 – 64 years, and ≥ 65 years. In case recruitment lags we will add external study sites. In such a scenario, University of Cincinnati and the facilities of the affiliated health systems UC Health, LLC and University of Cincinnati Physicians Company, LLC will follow the same randomization scheme. In case of other external sites, randomization will be stratified based on site in addition to the above-mentioned age-based stratification. As exploratory analysis, we will conduct analyses examining differences based on other prognostic factors and concomitant medications such as corticosteroids, hydroxychloroquine, azithromycin etc. An intent-to-treat analysis will be performed for the primary outcome.

16. Identification and access to source data

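### Hospital stay is counted from admission, so days before randomisation, which treatment cannot affect, enter the comparison between arms

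*Combined protocol and SAP*

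**What the plan says.** Section 8.5 defines the stay variable in days: it "will be recorded starting from the day of admission to the day of hospital discharge". It adds: "This parameter will only be used for analysis in patients who survive the hospital stay". Section 4.3 lists the variable under other outcome measures, below the primary and key secondary endpoints.

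Death has a different time origin. Section 8.5 states: "For non-survivors, the time from study initiation to death will also be recorded". Section 4.3 words that origin as the start of treatment. Either way, the clock for death starts with the study and the clock for stay starts before it.

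Hospital time before enrolment is expected. Section 5.1 describes screening through "chart reviews of the patients admitted on the COVID units", and Section 8.4 asks for a pregnancy test "if not already obtained during the hospitalization prior to study enrollment". The eligibility criteria in Sections 5.2 and 5.3 set no maximum interval between admission and randomisation. Section 15 and the SAP specify "computer-generated permuted block randomization stratified on age", with site added only if external sites join. Time since admission is not a stratification factor. Neither document gives an analysis method for hospital stay or an adjustment for days already spent in hospital.

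**The concern.** The interval from admission to randomisation is fixed before anyone is assigned to sirolimus or placebo. It is a baseline quantity, and the plan adds it to an outcome that will be compared between arms. In a large trial the two arms would have nearly the same average and little would follow. With 30 patients split 2:1, the averages can differ visibly by chance, and that difference is then reported as part of the difference in stay. Variation in the interval also usually widens the uncertainty around that difference. The trial is meant to inform a larger one, so an estimate of stay that contains days no treatment could change is a poorer planning input than it need be.

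**Working it through.** **The plan's own figures.** The documents give no SD, effect size or power for hospital stay, so there is nothing to reproduce for this outcome. The N = 30 justification concerns the primary endpoint only. With 0.50 of 10 against 0.25 of 20, SE = √(0.25/10 + 0.1875/20) = 0.185, and the 80% interval is 0.25 ± 1.2816 × 0.185, or 0.012 to 0.488. It excludes zero and does not depend on how stay is measured.

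**Inputs.**
- From the documents: 30 patients, 2:1, so 20 sirolimus and 10 placebo.
- Assumed: SD of days from admission to randomisation (SDpre) of 1, 2 or 3; SD of days from randomisation to discharge (SDpost) of 6; correlation ρ between the two, first 0 and then varied.

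**Step 1: chance imbalance in pre-randomisation days.** SE = SDpre × √(1/20 + 1/10) = 0.387 × SDpre. The probability of an absolute imbalance of at least 1 day is 2 × [1 − Φ(1/SE)].

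**Step 2: variance of stay from admission.** Variance = SDpre² + SDpost² + 2ρ·SDpre·SDpost, compared with SDpost² = 36 when the clock starts at randomisation. Equivalent N is 30 divided by the variance ratio.

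| SDpre (days) | SE of imbalance (days) | P(imbalance ≥ 1 day) | Variance, ρ = 0 | Ratio to 36 | Equivalent N |
|---|---|---|---|---|---|
| 1 | 0.39 | 1% | 37 | 1.03 | 29.2 |
| 2 | 0.77 | 20% | 40 | 1.11 | 27.0 |
| 3 | 1.16 | 39% | 45 | 1.25 | 24.0 |

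The SE of the arm difference in stay is √(36 × 0.15) = 2.32 days from randomisation. From admission it is √(37 × 0.15) = 2.36, √(40 × 0.15) = 2.45 and √(45 × 0.15) = 2.60 days.

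**Step 3: dependence on the correlation.** The variance penalty is zero when ρ = −SDpre/(2 × SDpost), that is −0.08, −0.17 and −0.25 for SDpre of 1, 2 and 3. At ρ = −0.3 the variances are 33.4, 32.8 and 34.2, all below 36. At ρ = +0.3 they are 40.6, 47.2 and 55.8, so the penalty grows. The imbalance SE in Step 1 does not depend on ρ.

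**Step 4: survivors only.** Section 8.5 restricts the variable to survivors, so the groups shrink if anyone dies. With 17 and 8 survivors, as an illustration, the imbalance SE becomes 0.43, 0.86 and 1.29 days, and the chance of a gap of at least 1 day is 2%, 24% and 44%.

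**The case against.** Admission to discharge is a clear, prespecified measure of total hospital stay. The outcome ranks low, no test is planned for it, and stay from randomisation can be computed later from dates already held. All of that is true, and it is why the point is minor. It is not a reason to keep pre-study days in the comparison.

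The more serious objection concerns correlation. A reader might infer that the admission clock always costs precision. The documents do not support that. Patients enrolled late in an admission may be closer to discharge, and a mild negative correlation is enough to remove or reverse the penalty. Likewise, the pre-study days are added in full, but their net expected effect on the reported difference depends on ρ. At ρ = −0.3, each extra pre-study day goes with 0.3 × 6/2 = 0.9 fewer later days (SDpre 2) or 0.3 × 6/3 = 0.6 fewer (SDpre 3), leaving a net 0.1 or 0.4 day. The sign of the correlation is unknown. This part of the objection stands.

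A reader might also infer that the definition biases the comparison towards one arm. It does not: the interval is settled before a blinded random assignment, so its expectation is the same in both arms. Whatever selection the survivors-only restriction brings is a separate matter, which a change of clock does not cure.

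Finally, Section 5.1 describes active chart screening and automated alerts on suspected cases, which suggests early enrolment without guaranteeing it. If SDpre is near 1 day, the effect is negligible.

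**Conclusion.** The point holds as a minor one. Pre-randomisation days are part of a between-arm outcome, nothing in the protocol or SAP limits them, balances them by design or adjusts for them, and the time-to-death clock starts later. The consequence is chance imbalance and, usually, some loss of precision. Its size runs from negligible (SDpre 1: about a 1% chance of a 1-day imbalance, variance up 3%) to noticeable (SDpre 3: 39%, variance up 25%). These figures rest on assumed SDs and on all 30 patients being analysed; the variance figures also assume independence of earlier and later stay. The imbalance figures do not need that last assumption. The primary endpoint and the sample size are unaffected.

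**What to change.** In Section 8.5, count hospital stay from randomisation (study Day 1) to discharge, in line with the time-to-death clock. If the first dose can fall on a later date than randomisation, name one of the two as the origin and use it for both durations, since Sections 4.3 and 8.5 now word the origin for death differently. Report days from admission to randomisation by arm as a baseline characteristic. Total stay from admission may still be given descriptively.

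The cost is a sentence or two. The present definition already needs the admission and discharge dates, and Day 1 is known for every patient, so no new data are collected.
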